#### 1.2 Trial Summary (less than 300 words) including background, objectives and trial plan.

Individuals with Type 1 diabetes (T1D) and sub-optimal glycaemic control are at high risk of developing diabetes complications. This burden of chronic disease and poor health can negatively impact the individual and the family and incurs high health care costs on health care systems and the community. Hence, it is vital to devise interventions to improve glycaemic control and potentially reduce the burden of chronic disease management.

The objective of this project is to utilize an automated insulin delivery (advanced hybrid closed loop) system to improve glycaemic control. Advanced Hybrid Closed Loop (AHCL) system has an automated insulin delivery dependent on sensor glucose readings; although it requires the user to administer meal boluses. HCL therapy was safe during in-home use by adolescents and adults with increased time in target, and reductions in HbA1c, hyperglycaemia and hypoglycaemia, compared to baseline. These results are encouraging and hence it would be valuable to test the effectiveness of HCL in patients with poor glycaemic control and this will be the first trial in this high risk subgroup of patients. This AHCL version includes automatic correction boluses.

We hypothesise that the automated insulin delivery will circumvent the significant glycaemic excursion associated with conventional therapy in patients with poor glycaemic control. Reduced adherence to diabetes self-management tasks is often associated with poor glycaemic control and this trial will address, in effect, the important question as to whether the challenge of managing AHCL is less than the challenge of routine treatment and will generate data that will inform approaches to enhance adherence.

We propose a 6 month multi-centre randomised controlled parallel design study (n=50) assessing the effect of AHCL in adolescents with sub-optimal glycaemic control and comparing this technology with standard care. The primary aim is to compare the change in HbA1c levels during 6 months of therapy with AHCL vs conventional therapy. Secondary outcomes (glycaemic, psychosocial, human factors analysis and health economics) will be measured and analysed.

#### 2. Rationale / Background

2.1 Summary of findings from previous clinical and non-clinical projects, relevant to this proposed trial. Include references to literature and data that are relevant to the trial and that provide background for the trial. *List references separately at the end of the protocol.* 

The incidence of type 1 diabetes (T1D) is increasing by around 3% each year with a prevalence of 1 in 300 (1). Despite modern treatment, complications of T1D and a reduced life expectancy continue to be a reality for patients. Fewer than a third of young patients in Australia reach a HbA1c of less than 7.5%, a target which has been shown to significantly reduce the development of complications associated with T1D(2). Individuals with T1D and poor glycaemic control are at high risk of developing diabetes complications (3) both in the short term (psychosocial stress, educational impact, hospitalisations for diabetic ketoacidosis or severe hypoglycaemia), and in the long term (for example kidney failure, blindness, heart disease, and peripheral vascular disease requiring amputations). This burden of disease would thereby incur higher health care costs. An increase in HbA1c by 1percentage-point will, on average, lead to a 6.0% increase in diabetes-related medical costs for type 1 diabetes (4). Attempts to aggressively manage blood glucose levels in order to avoid long-term complications are limited by the fear of hypoglycaemia and anxiety for patients and their caregivers, affecting quality of life, and promoting behaviours aimed at avoiding hypoglycaemia. These actions lead to hyperglycaemia, placing patients at higher risk of developing long term complications. Likewise, T1D affects cognitive function, social function, and places a large health and economic burden on families and the community(1). In 2008-2009, \$214 million of healthcare expenditure was for Type 1 diabetes (5). Patients with poor glycaemic control are likely to disproportionally contribute to healthcare costs. For all these reasons, it is essential to develop new therapies and device interventions that can improve glycaemic control in this patient group to reduce the burden of disease both on the patient and community.

We recently demonstrated that continuous subcutaneous insulin infusion (CSII) is an effective tool in providing sustained glycaemic improvement in adolescents on multiple daily insulin injections willing to trial insulin pump therapy. The cohort had a reduction of HbA1c by 1.5% at 12 months (de Bock et al, accepted JDST 2018). Hence, as future technologies such as hybrid and fully closed-loop systems become available, patients with sub-optimal glycaemic control should be considered for inclusion in clinical trials, as by virtue of their baseline HbA1c as they potentially have the most to gain.

Closed-Loop technology integrates continuous measurement of interstitial glucose levels from a glucose sensor, a pump for delivering insulin and an algorithm that determines insulin delivery without patient intervention. It offers the potential to circumvent the significant glycaemic excursions associated with conventional therapy. Superior glycaemic control has been demonstrated in many inclinic studies, diabetes camp studies, hotel studies, short term and long term outpatient studies with lower rates of hypoglycaemia when compared to current diabetes management strategies (6-11). Hybrid closed loop (HCL) has an automated insulin delivery based on sensor glucose feedback system; still requiring the user to administer mealtime bolus insulin. HCL therapy was safe during inhome use by adolescents and adults with increased time in target, and reductions in HbA1c, hyperglycaemia and hypoglycaemia, compared to baseline (7). We have conducted pilot studies using the Medtronic hybrid closed loop system and initial home studies have shown promise of its potential for more prolonged controlled trials (12, 13). We are currently investigating the Medtronic 670G (version 3.0) hybrid closed loop system in a large multicentre trial in Australia, comparing it's efficacy to standard treatment, and assessing a wide range of outcomes (2016087EP). This study will use the Medtronic 670G 4.0, which includes an updated (advanced hybrid closed loop AHCL) algorithm. The 670G Version 4.0 (AHCL) insulin pump is based on the FDA approved/CE Marked 670G insulin pump. The 670 Version 4.0 (AHCL) insulin pump uses the same hardware as the 670G pump and enhancements relative the the 670G pump listed includes the in section 2.2. In view of the recall on Medtronic Minimed™ 670G 4.0 insulin pumps with clear retainer rings, the study will use the Medtronic Minimed™ 780G insulin pump with the same algorithm, which has the added feature of bluetooth connectivity to allow remote monitoring of glucose levels. For the trial, to maintain the same functionality of the pump, we will use the MiniMed™ 780 pump without using bluetooth feature.

The use of closed loop technology has not been assessed for patients with poor glycaemic control and this will be the first trial in this important subgroup of patients. **This proposal explores the hypothesis that automated insulin delivery will result in improved glycaemic control.** This is an important patient group to study, as they have the greatest potential for improvement in glycaemic outcomes. Individuals in this high risk group also have the potential for improved wellbeing and reduced burden of disease from diabetes complications and health economic impacts which will be analysed in the study. We will explore the impact of this system on quality of life, fear of hypoglycaemia, diabetes distress and acceptance and satisfaction with the use of diabetes technology. Data will be collected to quantify the economic impact of AHCL compared to standard therapy and extrapolated. The trial will also look into the potential risks with AHCL therapy. The risk of poor treatment adherence by this group will be closely monitored and will address the hypothesis of whether the challenge of managing AHCL therapy is less than the challenge of routine treatment and will generate data that will inform the clinical indications for different diabetes management regimens and delivery of diabetes education in an era of rapidly advancing technology. Acute deterioration in diabetic retinopathy is a known potential risk when glycaemic control is rapidly optimised, as such this will be closely monitored in the trial (14).

Vascular complications are a major cause of morbidity and premature mortality in people with diabetes, due to traditional (adiposity, dyslipidaemia, hypertension, smoking, poor glycaemic control) and novel vascular disease risk factors (subtle changes in lipoproteins, such as oxidation and nonenzymatic glycation, Advanced Glycation End Products (AGEs), oxidative stress, inflammation, altered angiogenesis, prothrombotic tendencies, glycaemic variability, impaired vasoregulation, and more recently recognised molecular changes like telomere length, activity of telomerase (the enzyme which controls telomere length), microRNAs and DNA methylation. Collection of suitable samples and their analyses are particularly relevant to this study as vascular damage starts early in life, particularly in individuals with poor glycaemic control. Improved metabolic control may at least partially reduce adverse risk factor profiles. Furthermore, we have cross-sectional data demonstrating improved vascular function and a less adverse novel vascular risk profile in insulin pump treated T1D patients and evidence that molecular markers can be improved by existent and emerging drug therapies.

2.2 Name and description of the intervention or product(s) used in this trial, including investigational product(s) and comparator product/s (if applicable). Include status of product registration (i.e. registration on Australian Therapeutic Goods Registry, or equivalent).

The **Medtronic advanced hybrid closed loop system** is an investigational device which compromises an advanced closed loop algorithm with the compatible, glucose sensor and glucose sensor transmitter.

The algorithm uses a modified proportional integrative derivative (PID) model, with insulin feedback and additional safety features. The algorithm receives glucose data every 5 minutes from the sensor, and a "basal rate" insulin delivery is computed and adjusted every five minutes. Therefore, standard "basal" insulin that is pre-programmed in regular insulin pump therapy is replaced by the algorithmderived insulin delivery (given as a micro-bolus every 5 minutes). Meals will still be announced, and an insulin bolus delivered according to the individualised patient's carbohydrate ratio.

The system in Manual Mode can be programmed to automatically suspend basal insulin delivery for up to two hours when the sensor glucose falls below a predefined or predicted threshold value. In Auto Mode, the system can be programmed to automatically calculate the insulin dose based on information received from continuous glucose monitoring (CGM).

The AHCL has the following enhancements from the commercial Medtronic 670G pump with HCL:

- Additional setpoint option of 5.6 mmol/L (in addition to 6.7 mmol/L and temp target of 8.3 mmol/L). Correction target is 6.7 mmol/L for both 5.6 mmol/L and 6.7 mmol/L setpoints.
- Automatic correction bolus delivery when the pump has been delivering at the maximum allowable basal rate and sensor glucose remains elevated above the correction target when pump is in Auto Mode
- Ability to make therapy adjustment based on sensor glucose values without the requirement for a confirmatory self-monitoring blood glucose (SMBG) measurement
- Other updates to the Auto Mode algorithm intended to reduce the frequency of exits from Auto mode and further minimize glucose excursions.

The MiniMed™ 670G Version 4.0 (AHCL) insulin pump uses the same hardware as the MiniMed™ 670G pump with the advanced algorithm. In view of the recall on insulin pumps with clear retainer rings, the study will use the 780G insulin pump with the same algorithm, which has the added feature of bluetooth wireless communication with the compatible devices in the MiniMed™ 780G System connectivity.

The MiniMed™ 780G Pump works with the following major components: 1) Continuous Glucose Monitoring (CGM) that includes the Guardian Link (3) Transmitter that is connected to the Guardian Sensor (3) to receive sensor glucose values at 5 minute intervals; 2) blood glucose meter (Roche Accu-Chek®) that will be used to calibrate the sensor and has the ability to send blood glucose values

wirelessly as a convenience to the user; 3) MiniMed™ Clinical App to allow upload of data wirelessly, for sharing of glucose levels

To maintain the same functionality as the 670G 4.0 pump for the trial, we will not be using the Minimed™ Clinical App.

**Glucose monitoring:** All participants will be issued with the CONTOUR® NEXT LINK 2.4 from Bayer. This glucose monitor requires CONTOUR PLUS test strips.

Participants randomised to AHCL will be issued with a study meter, Roche Accu-Chek®, this allows for data to be directly sent to the MiniMed 780G insulin pump.

**CareLink Software**: CareLink is a Medtronic web-based platform which is used for uploading insulin pump data. The Medtronic 670G can be uploaded, using the CONTOUR® NEXT LINK 2.4, which is plugged into the USB port of a PC. The software is Apple and Windows compatible. The MiniMed™ 780G can be uploaded to CareLink via the Blue Adaptor (also know as the BLE dongle). The Blue Adapter is a commercial-off-shelf-component provided by Career Technologies. The Medtronic accessory number is ACC-1003911. The Blue Adapter is not a medical device thus no labeling is needed. Insulin pump data is then accessible for download by the investigators.

**Blinded CGM** will be collected twice during the study (baseline –for two weeks, and for two weeks at the end of the study). A 4th generation sensor will be inserted and a glucose transmitter connected. Participants will be required to record finger prick glucose levels at least four times a day. CGM data is collected by uploading the transmitter and finger prick values from the CONTOUR® NEXT LINK 2.4 from Bayer.

#### 3. Trial Aims / Objectives / Hypotheses

3.1 Detailed description of the specific primary and secondary objectives and the purpose of the trial. Describe any hypotheses that will be tested.

#### Aims

The primary aim of the study is

1) To determine the effect of hybrid closed loop on the change in glycated haemoglobin (HbA1c) in adolescents with suboptimal glycaemic control (HbA1c>8.5%) and comparing this technology with standard care.

The secondary aims of the study are

- 2) To determine the effect of hybrid closed loop on percentage time in range compared to standard therapy
- 3) To determine the effect of hybrid closed loop on *psychological and social well-being* compared to standard care
- 4) To determine the effect of hybrid closed loop on glycaemic parameters on hypoglycaemia and hyperglycaemia compared to standard therapy
- 5) To determine the effect of hybrid closed loop technology on *retinopathy*
- 6) To determine the effect of hybrid closed loop technology on the metabolic biomarkers
- 7) To determine the cost effectiveness of hybrid closed loop technology compared to standard therapy in long term.
- 8) To determine the technology-user" interactions ("human factors") to improve translational strategies

#### Hypotheses:

- 1) HCL will improve glycaemic control as assessed by HbA1c.
- 2) HCL will have a positive impact on quality of life and fear of hypoglycaemia as determined by participant/parent questionnaires.
- 3) Closed loop technology by improving control could potentially deteriorate retinopathy
- 4) HCL will be a cost-effective intervention for the management of type 1 diabetes compared to standard treatment.

#### 4. Trial Design

# The scientific integrity of the trial and the credibility of the trial data depend substantially on the trial design and methodology.

4.1 Primary endpoints and the secondary endpoints, if any, to be measured during the trial and how they will be measured. *For further information refer to the TGA* "Note for Guidance on Good Clinical Practice (CPMP/ICH/135/95)" 2000.

#### Primary endpoint:

A) Glycaemic control as measured by change in HbA1c collected at baseline, 3 and 6 months post randomisation

#### Secondary endpoints

- B) Psychosocial well-being
  - 1) Functional health status EQ-5D-3L (12 to ≤25yrs)
  - Diabetes specific quality of life: PedsQL Child version (<13 yrs), Adolescent version (13 to <18yrs) and young adult version (18 to ≤25yrs).

  - Fear of hypoglycaemia: Hypoglycaemic Fear Survey-II Worry scale: 17-≤25years. Children's Hypoglycaemia Fear survey 12 to <17yrs.

  - 4) Impact and Satisfaction: The Diabetes Technology Questionnaire, Baseline and Follow-up version (all ages)
  - 5) Diabetes distress: Problem Areas in Diabetes (Paediatric version 12 to <18yrs, Standard version ≥18yrs, Parent version)
  - 6) Hypoglycaemia Awareness: Hypoglycaemia Awareness Scale (Gold Score) (all ages)
  - 7) Generalized Anxiety Disorder-7 and Patient Health Questionnaire-9 (12 to 25 years)
  - 8) INSPIRE: Perceived benefits and burdens of automated insulin delivery (all ages Intervention only)
  - 9) Physical activity: The Active Australia Survey (all ages)
  - 10) Semi structure interview (all ages post study only)
- C) *Glycaemic outcomes:* -Percent time in range
- D) -CGM data: (time in hypoglycaemia, time in range, and time in hyperglycaemia)
  - a. % CGM Time <2.8 mmol/L
  - b. % CGM Time <3.3 mmol/L
  - c. % CGM Time <3.9 mmol/L
  - d. % CGM Time 3.9-7.8 mmol/L
  - e. % CGM Time >10.0 mmol/L
  - f. % CGM Time >13.9 mmol/L
  - g. % CGM Time >16.7 mmol/L
  - h. Standard Deviation and Coefficient of Variation of CGM values
- E) Changes in retinopathy scores and retinal microvascular structure (arteriolar or venular dilation, increased vascular fractal dimension, branching and tortuosity)
- F) Human factors:

Describe participant technology interaction, adherence patterns and approaches to improve interaction.

G) Health-economic

Report the health economic impact of the MiniMed ™ 670G / 780G Insulin Pump Hybrid Closed Loop System Vs standard therapy. The following data points will be used as part of the economic analysis:

- 1) QALYs calculated from the EQ-5D-3L
- 2) Hypoglycaemic events and HbA1c
- 3) Participant reporting on work interruption
- 4) Investigator reporting time spent on training, education and support, by the type of health professional resource used
- 5) Diabetes management consumables (glucose strips, ketone strips, batteries, sensors, site dressings, lancets, needles, insulin).

4.2 Type (e.g. phase, pilot) and design (e.g. double-blind, placebo-controlled, parallel design) of the trial to be conducted and a schematic diagram of the trial design, procedures and stages (e.g. initial assessment, run-in, pre-randomisation assessment, randomisation, treatment phase, end-of-treatment assessment, washout, cross-over, alternative treatment, post-treatment assessments, trial exit).

This is a **prospective multicentre randomised controlled, two-arm unblinded, parallel study** in free-living conditions, in adolescents with type 1 diabetes on insulin pump therapy. Participants are randomized in two groups; either the control group (standard therapy) or the intervention group (advanced hybrid closed loop). The control group will be participants on insulin pump therapy with or without CGM (continuous glucose monitoring).

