#### 5. Source and Selection of Participants

5.1 **Source of participants** - research population, sample size, source, and sampling frame (if possible, split by site if multicentre trial).

Eligible participants will be identified through the Western Australian Children's Diabetes Database (WACDD) and state specific databases. A generic invite with the information sheet will be sent electronically. Participants will also be identified during their clinic visits. We may also use advertisements, notices, and/or media to recruit participants. Examples include flyers posted in public settings, newspaper ads, and radio and television advertisement. All advertisements and recruitment materials (e.g., video, audio, and telephone scripts) will be submitted to HREC for prior approval. Indirect recruitment will also be conducted in these sites with authorised access request: Fiona Stanley Hospital, Sir Charles Gairdner Hospital, and Rockingham General Hospital.

- 5.2 **Participant inclusion criteria.** Describe appropriate criteria for special risk populations (e.g. women of reproductive age, participants with disease states or organ impairment).
  - 1. Type 1 diabetes (diagnosis consistent with American Diabetes Association Classification of Diabetes Mellitus, diagnosed at least 1 year ago)
  - 2. Fasting C peptide <0.1nmol/L (in the absence of hypoglycaemia)
  - 3. Pump therapy for at least 6 months
  - 4. Age 12 to 25 years
  - 5. Recent HbA1c > 8.5% in the last 3 months
  - 6. Mean HbA1c > 8.5% for 6 months
  - 7. Willing to follow study instructions
  - 8. Willing to perform  $\geq$  3 finger stick blood glucose measurements daily
  - 9. Willing to perform required sensor calibrations
  - 10. Capable of reading and understand instructions in English
  - 11. Living in an area with internet and cellular phone coverage
  - 12. Minimum daily insulin requirement (Total Daily Dose) of greater than or equal to 8 units
- 5.3 **Participant exclusion criteria.** May include conditions that increase the risk to the participant, that interfere with the participant's ability to give informed consent or interfere with a participant's ability to comply.
  - 1. Participants using closed loop therapy within the past 3 months
  - 2. Severe DKA in the 6 months prior to the screening visit
  - 3. Use of any non-insulin glucose-lowering agent within the past 3 months

- 4. Commenced CGM in the 3 months prior to the screening visit

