# 6.2 The **medications/treatments permitted** (including rescue medication) and not permitted before and/or during the trial.

For severe hypoglycaemia, intramuscular glucagon can be administered.

For ketosis > 0.6 mmol/l with blood glucose > 15mmol/l, insulin (short-acting) is administered with a pen.

This is taught to every family at the time of diagnosis of T1D and review of their knowledge is established in subsequent clinic follow-ups.

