#### Extension phase

The extension phase will allow device access to all participants taking part in the study and will allow safety data to be collected over a longer period of time. The effects noted during this period are not of primary interest and the approach to analysing extension phase data will be largely exploratory.

We will describe the patterns in primary and secondary outcomes from 6 months to 12 months in Group A (receiving the intervention at both time points) and compare the 6-month post-intervention effect size in Group B to that observed in Group A during the primary study phase.

Primary and secondary outcome scores, paired differences, and their 95% confidence intervals will be presented.

9.2 The number of participants planned to be enrolled (if possible, include number at each site). Document the reason for choice of sample size, including reflections on (or calculations of) the power of the trial and clinical justification.

The power calculation is for a parallel study design with two groups of equal size.

The power calculation is for a parallel study design with two groups of equal size. Based on information in the WA population-based database and current data (de Bock et al, accepted JDST 2018), we expect a between group difference of 1.5% in HbA1c at 6 months with a SD of 1.7% for both groups. With alpha set at 0.05, 22 subjects would be required in each group to have 80% power to detect a difference of 1.5%. It is assumed the total dropout rate will be up to 15%, so we plan to recruit 50 subjects in total.

- 9.3 The level of significance to be used. P-values <.05 will be considered statistically significant and 2-sided P-values will be reported.
- 9.4 Procedures for reporting any deviation(s) from the original statistical plan (any deviation(s) from the original statistical plan should be described and justified in the protocol and/or in the final report, as appropriate).
   Any deviations to the original statistical plan will be reported to relevant ethics committees, governance committees, the Australia New Zealand Clinical Trial Register (ANZCTR), the DSMB and the manuscript.
- 9.5 The selection of participants to be included in the analyses (e.g. all randomised participants, all dosed participants, all eligible participants, or all evaluable participants).

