The primary analysis will take a modified intention-to-treat approach, with all randomised participants who attended at least one visit following randomisation being included in the analysis. A secondary analysis using a 'per-protocol' sample (defined as participants with over 70% adherence to pump and sensor) will also be conducted.

9.6 Information on how data will be managed, including coding for computer analysis and data handling (collection, storage, maintenance, security and archiving). Include details regarding these processes if the data is sent off-site (e.g. encryption). *Clinical trial records should be retained for a minimum of 15 years from the completion of the trial.* 

All data will be anonymised and will not be able to be linked back to any individual participant. Data will be stored on secure servers and electronic device capture systems with secure access for study staff only and all data will be stored in an anonymised form that cannot be linked back to the original participant. All data will be stored for 25 years in line with GCP requirements on secure servers. Hard copies of patient notes will be stored in secure filing cabinets at each site and archived in secure facilities' at the end of the trial.

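### The per-protocol rule in Section 9.5 does not fit the control arm: it cannot place controls without CGM, and it keeps controls who start a closed-loop system

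*Protocol*

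**What the plan says.** Section 4.2 describes the comparator: "The control group will be participants on insulin pump therapy with or without CGM". Section 4.9 adds that these participants follow their usual diabetes care.

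Section 5.3 excludes "Participants using closed loop therapy within the past 3 months" and "Use of any non-insulin glucose-lowering agent within the past 3 months". Both criteria look back from entry. Section 6.2, whose heading asks what is permitted and not permitted before or during the trial, names two measures: "For severe hypoglycaemia, intramuscular glucagon can be administered", and pen insulin for ketosis. It lists nothing as disallowed.

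Medications appear in the Visit 1 data list. The Visit 5 and Visit 8 lists contain HbA1c, insulin dose, pump upload in both groups, sensor data for CGM users and a clinical review. They have no item for medications or for a change of delivery system.

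Section 9.5 makes a modified intention-to-treat analysis primary and adds a secondary per-protocol sample, "defined as participants with over 70% adherence to pump and sensor". It gives no separate criterion for each arm and no condition on the treatment received.

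**The concern.** A per-protocol criterion should describe following the assigned regimen. Pump and sensor wear does so for the AHCL arm, where the system needs both. It does not for the control arm, where a person can follow the assigned regimen fully and never wear a personal sensor.

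Two misclassifications follow. A control without CGM has no sensor adherence to measure, so that person fails the rule or cannot be placed. A control who moves to a commercial closed-loop system, and uses it regularly, wears pump and sensor together and so tends to pass. The rule can thus remove controls who stayed on the comparator and keep controls who left it.

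At stake are the direction of bias in a named secondary analysis and the reading of the main result. If a reduced effect is seen, the report would need a count of controls who started such treatments, and no named variable supplies it.

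**Working it through.** **Where the passages meet**

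| Control after randomisation | Regimen as described in Section 4.2 | Result under the Section 9.5 rule |
|---|---|---|
| Pump, no CGM | On it | Fails or cannot be classified |
| Pump with CGM worn over 70% | On it | Kept |
| Starts closed loop, sensor worn over 70% | Has left it | Kept |
| No CGM, starts a non-insulin agent | Not addressed | Fails or cannot be classified |
| CGM worn over 70%, starts a non-insulin agent | Not addressed | Kept |

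**Is closed loop a real route?** Section 2.2 refers to a commercial Medtronic 670G with hybrid closed loop, and the background questionnaire in the appendices lists the 670G among previous pumps. Someone who stopped such a system more than 3 months before entry is not excluded by that criterion, and no written rule prevents a later start.

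**Is a start captured?** Non-insulin agents have no named item after Visit 1. For closed loop, pump uploads in both groups may show automated delivery, but no variable is named and CareLink is described only for Medtronic pumps. The follow-up Diabetes Technology Questionnaire asks which devices are in use. At Visits 5 and 8, however, it is given only to the AHCL arm, and its device list has no closed-loop box.

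**The plan's own figure.** Section 9.2 states "22 subjects would be required in each group to have 80% power to detect a difference of 1.5" percentage points of HbA1c, with SD 1.7; Section 9.3 says "2-sided P-values will be reported". A two-sample t-test at two-sided alpha 0.05 gives 79.7% power with 21 per group and 81.6% with 22, so 22 reproduces. The 1.5 points are used below only as a scale.

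**Illustration.** The protocol gives no switching rate, wear rate or gain for a switcher, so these are assumed:
- p = share of controls who switch to closed loop
- f = share of controls who pass the 70% rule, with all switchers passing
- e = HbA1c gain of a switcher, in points
- AHCL effect against a non-switching control = 1.5 in both analyses

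Switchers among per-protocol controls = p/f. Intention-to-treat difference = 1.5 − e·p. Per-protocol difference = 1.5 − e·p/f.

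For p = 0.10 and e = 1.5:
- Intention to treat: 1.5 − 0.15 = 1.35
- f = 0.60: p/f = 0.167, so 1.5 − 0.25 = 1.25
- f = 0.40: p/f = 0.25, so 1.5 − 0.375 = 1.125

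For p = 0.10 and e = 0.5:
- Intention to treat: 1.5 − 0.05 = 1.45
- f = 0.60: 1.5 − 0.083 = 1.417
- f = 0.40: 1.5 − 0.125 = 1.375

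With 25 controls (half of 50), p = 0.10 means two or three people among the 10 to 15 controls who pass.

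**How fragile is the ordering?** The 70% rule also removes low-adherence AHCL users. Let E be the AHCL effect among those kept. For p = 0.10 and e = 1.5, the per-protocol difference lies below 1.35 only if E < 1.35 + 1.5·p/f. That bound is 1.60 at f = 0.60 and 1.725 at f = 0.40. If adherent users gain more than this, the per-protocol difference is the larger one.

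**The case against.** The strongest reply is that the comparator is standard care. A treatment change made in ordinary care is then part of the comparator, and the primary analysis rightly keeps it. That stands, and it is why neither control-arm care nor the primary analysis needs to change. It also means that lost power in the intention-to-treat comparison is not part of this point.

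A reader might infer that the per-protocol set is meant to strip out non-protocol treatment. Section 9.5 gives no such purpose; it states only an adherence rule. The defect is that this rule does not describe adherence in the control arm.

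A reader might also infer that closed-loop switches go unseen. The uploads in both groups, the sensor data and the clinical review may well reveal them. What is missing is a named variable and a start date. Nor is every control who starts a non-insulin agent kept as per-protocol: one without CGM is not.

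The sensor in Section 9.5 could be read as the blinded study sensor, which controls also wear for short periods. The section does not say so. That reading would make controls without CGM classifiable but would still not remove a control on closed loop.

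Uptake may be low. No passage says that controls could readily obtain closed loop, and the offer of AHCL at six months lessens the incentive. This bears on size, which is assumed here.

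Finally, detailed analysis sets and data fields are often left to a statistical analysis plan. Here, though, the protocol itself states the rule and the visit lists, and a later plan cannot restore a start date that nobody recorded.

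**Conclusion.** The concern holds for the per-protocol definition and for the missing data items, and no further. Section 9.5 applies one pump-and-sensor rule to both arms although controls need not have a sensor. As written, it drops or cannot place controls without CGM and keeps controls who start closed loop and wear the sensor. The secondary comparison can therefore be pulled toward no difference.

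Its size cannot be derived from the documents. The range of 1.12-1.25 against 1.35 rests on 10% switching, a full 1.5-point gain (an upper bound), all switchers passing, 40-60% of controls reaching 70% wear, and an AHCL effect unaffected by the adherence rule. With a 0.5-point gain the shift is small (1.38-1.42 against 1.45), and a larger effect in adherent AHCL users can reverse the ordering. That the per-protocol result would be the more diluted one is possible, not shown.

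The severity is minor: only a secondary analysis and the interpretation of the result are affected.

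**What to change.** 1. Leave control-arm care and the modified intention-to-treat analysis unchanged.
2. At Visits 5 and 8, in both arms, record the start date of any closed-loop system, CGM or non-insulin glucose-lowering agent, and report the counts per arm. Uploads already taken may supply part of this.
3. In Section 9.5, state the per-protocol criteria by arm. Apply the sensor-wear criterion to the AHCL arm only. For controls, require that the participant stayed on pump therapy, whether or not CGM was used, and did not start closed loop or a non-insulin agent before Visit 8.

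These criteria govern an analysis set. They do not say which treatments a participant may receive; that remains for the sponsor to state.

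The cost is one data item at two existing visits and a short rewording of Section 9.5. The statistical downside is that the per-protocol comparison is selected on behaviour after randomisation, by a different criterion in each arm, and that behaviour may be related to glycaemic control. It should be reported as supportive only.
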